To endeavor to achieve a sample of at least 50 completed surveys, recruitment will remain open for a minimum of 3 months and up to 6 months in each country, and will not be closed early even if 50 completed surveys have been reached sooner. Metrics will be tracked to monitor survey progress (e.g., number of eligible/ineligible HCPs, number of completed surveys). Depending on response rates, follow-up reminders will be sent to non-respondents to achieve the target sample size. If after two reminders the target sample size has not been reached, the pool of potential HCP prescribers will be supplemented through additional outreach based on internet research or outreach through applicable professional societies, inclusion of additional countries within the European Union (EU)/European Economic Area (EEA), or extension of the survey period. The local teams of medical scientific liaison from Sanofi may also support the survey by reaching out to some of the HCPs contacted and whom they may already know or visit, so to encourage their participation.

The survey may be conducted in up to 2 waves. In the event that the survey has been open for 6 months in all countries and 30 completed surveys have not been achieved, with a minimum

of 10 of those having been completed by ENJAYMO™ prescribers, a second wave of the same survey will be conducted 6 to 12 months later.

Invitations to participate in the survey may be sent to up to 1,000 HCPs by either email (preferred) or by post mail (if email is not available) using the available contact information. The invitation letter will include information about the survey, a unique code, and instructions for accessing the survey. The unique code will be used to track who has already completed a survey so that reminders are only sent to HCPs who have not yet completed the survey.

As an acknowledgement of their time and valuable input, HCPs who complete the survey will receive fair market value (FMV) compensation if allowed, feasible, and in accordance with local regulations.

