	Knowledge of current local vaccine guidelines or recommendations in patients with persistent complement deficiencies	Checked “true” to question 5
Knowledge of important potential risks of serious infections from encapsulated bacteria	Knowledge that Neisseria meningitides infection warrants caution	For question 6: “Checked” Neisseria meningitides infection warrants caution
	Knowledge that Hemophilus influenza infection warrants caution	For question 6: “Checked” Hemophilus influenza infection warrants caution
	Knowledge that Streptococcus pneumoniae infection warrants caution	For question 6: “Checked” Streptococcus pneumoniae infection warrants caution
	Knowledge that urinary tract infection warrants caution	For question 6: “Checked” urinary tract infection warrants caution
HCPs’ knowledge of the need to monitor and counsel patients	Knowledge to monitor for signs and symptoms of serious infections	Checked “yes” to question 7b
	Knowledge of caution in patients with chronic infections (Hep B, C or HIV)	Checked “yes” to question 7c
	Knowledge to counsel patients about the risks including meningitis	Checked “yes” to question 7d
	Knowledge that monitoring for kidney damage is not indicated	Checked “no” to question 7a
	Knowledge that thyroid function does not need to be assessed	Checked “no” to question 7e
	Knowledge that patients do not need to be counselled to monitor heart function	Checked “no” to question 7f
HCPs’ knowledge to counsel patients to monitor for symptoms of relevant serious infections	Knowledge to counsel patients to seek	Checked “false” to question 8c
	Knowledge that swelling in legs, ankles and feet is not a symptom of interest	Checked “false” to question 8e
	Knowledge that polyuria, dry mouth and blurred vision is not a symptom of interest	Checked “false” to question 8f
Assess whether HCPs received and read the ENJAYMO™ Physicians’ Guide	Received ENJAYMO™ Physician’s Guide	Checked “yes” to question 1
	Read ENJAYMO™ Physician’s Guide	Checked “yes” to question 2
Primary source of the indication, risk and	Response choices: SmPC, ENJAYMO™ Physician’s Guide, Professional society or	Checked each of the response choices to question 9

Study Objective Domains Assessed	Corresponding variable	Operational definition/derivation “Calculated as the percentage of HCPs who”*
recommendations for ENJAYMO™	congress, EMA website, Clinical practice guidelines, Other	

*Denominator to include “I don’t know/am not sure”

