9.8 Data Management

Survey data collection will be completed on-line in Conformat, a software platform specifically designed for the creation and delivery of multi-lingual surveys. Data collected will be stored at secure servers and will be maintained to ensure compliance with applicable local and national regulations.

Response sets for multiple-choice questions will be randomised to minimise bias. To minimise likelihood that respondents would look up answers and/or discuss the survey while taking it, respondents will be asked to complete survey in 1 sitting and will not be allowed to revise their answers after they advance to the next question.

Survey database lock is anticipated to occur shortly after the survey is closed in all countries. To reduce opportunity for bias, survey respondents will not be contacted to clarify or revise their responses to knowledge assessment-related questions.

Data management will be in accordance with the ICON's standard operating procedures (SOPs). Additional details regarding data collection, management of missing data, data storage, and validation procedures will be detailed in the survey manual and statistical analysis plan (SAP).

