9.11 Limitations of the Research Methods

A primary limitation of this cross-sectional survey is potential selection bias due to use of a convenience sample and/or low response rates. Moreover, the rarity of CAD and the relatively recent approval (meaning reimbursement in many EU countries may not yet or may only recently be available) may compromise the ability to identify a sufficiently large number of ENJAYMO™ prescribers to complete the survey. Therefore, the survey will be conducted amongst HCPs who treat CAD and were sent the ENJAYMO™ Physician's Guide, rather than limiting the survey to only ENJAYMO™ prescribers. Analyses will be performed stratified by ENJAYMO™ prescribing status.

The impact of selection bias can be minimized through robust outreach to recruit a representative sample of HCPs who have received the ENJAYMO™ Physician's Guide. For this survey, to minimize selection bias, HCPs from a broadly representative sample of European countries, geographically and via market-share, will be invited to participate. Countries in the EEA where the product is expected to be commercially available for at least 6 months may be included.

Generalizability of the study results may be limited in that the study population is based on a convenience sample. To improve generalizability, all HCP potential prescribers from included countries who were sent the ENJAYMO™ Physician's Guide, will be invited to participate in the survey (where sharing HCP contact information is allowed/available). To further endeavor to minimize selection bias:

- HCPs who have not responded will receive up to two reminders to encourage their participation.
- The HCP eligibility criteria are limited to target a broad population of HCPs available to prescribe ENJAYMO™.
- Where appropriate, HCPs will be offered a small reimbursement, based on FMV, for their time to complete the survey.

- Where HCPs are not able to commit to completing the survey, they will be provided the option to respond to one question indicating their reason for not participating in the survey.

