[Preamble 1]: These questions are about the risks of serious infections and meningococcal infections associated with ENJAYMO™ (sutimlimab). Please be sure to review all response choices for each question before answering each question. Please note that you will only be able to move forward in the survey as you complete each question.

CORRECT RESPONSES ARE CHECKED ✓

1. Did you receive the “ENJAYMO™ Physician’s Guide” that provides information to minimise the risks of serious infections and meningococcal infections associated with product use?
 - Yes
 - No
 - I don’t know/am not sure

2. Did you read the “ENJAYMO™ Physician’s Guide” that provides information to minimise the risks of serious infections and meningococcal infections associated with product use?
 - Yes
 - No
 - I don’t know/am not sure

3. ENJAYMO™ (sutimlimab) is indicated in adult patients with cold agglutinin disease (CAD) for the treatment of (Check all that apply) **RANDOMIZE ORDER OF THE FIRST 5 RESPONSES**
 - Hemolytic anaemia
 - Jaundice
 - Cardiac arrhythmia
 - Nausea and vomiting
 - Cold agglutinin syndrome
 - I don’t know/am not sure

4. ENJAYMO™ (sutimlimab) should only be prescribed to patients who have received appropriate vaccinations, especially against encapsulated bacteria.
 - True
 - False
 - I don’t know/am not sure

5. Are you familiar with current local guidelines or recommendations in patients with persistent complement deficiencies for meningococcal conjugate vaccine(s), meningococcal serogroup B vaccine(s), and pneumococcal vaccine(s)?

Yes
 No
 I don't know/am not sure

6. According to the ENJAYMO™ (sutimlimab) **Summary of Product Characteristics** and the “**ENJAYMO™ Physician’s Guide**”, which of the following warrant specific caution when using ENJAYMO™ (sutimlimab)? Please select all that apply.

Neisseria meningitides infection
 Hemophilus influenza infection
 Streptococcus pneumoniae infection
 Urinary tract infection
 All of the above
 I don't know/am not sure

7. According to the “**ENJAYMO™ Physician’s Guide**”, which of the following are important activities that are necessary when using ENJAYMO™ (sutimlimab):

		Yes, needs to be monitored	No, does not need to be monitored	I don't know/am not sure
A	Monitor patients for kidney damage			

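### Question 2, and to a lesser extent Question 1, has no time anchor, so a first reading of the Guide prompted by the survey cannot be told apart from reading after dissemination

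*Protocol*

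**What the plan says.** Protocol Annex 3 fixes the wording. Question 1 asks "Did you receive the “ENJAYMO™ Physician’s Guide” that provides information to minimise the risks of serious infections" and so on; Question 2 asks "Did you read the “ENJAYMO™ Physician’s Guide” that provides information to minimise the risks of serious infections and meningococcal infections associated with product use". Both offer yes, no and don't know. Neither refers to a date or to the survey invitation, and no later question dates receipt or reading. Question 9 asks only for sources of information.

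Protocol Table 9-1 (Section 9.2.2) defines received as "Checked “yes” to question 1" and read as "Checked “yes” to question 2". Section 9.2.2 lists receipt and reading as a secondary endpoint reported as a distribution. Section 9.9.1.2 uses reading or use of the Guide as a stratifier for the knowledge levels.

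On how HCPs are approached:
- The survey starts 6 to 18 months after the Guide is disseminated in a country and stays open for 3 to 6 months per country and wave (Section 9.3).
- Section 9.1.1 states: "The invitation letter will include information about the survey, a unique code, and instructions for accessing the survey". The sponsor's liaison staff may also contact some of the invited HCPs.
- Section 9.11 states: "HCPs who have not responded will receive up to two reminders to encourage their participation".
- The study title names the Guide, and the on-screen introduction in Annex 3 presents it as the thing under evaluation before Question 1 appears.

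Section 9.8 asks for completion in one sitting and bars changes to earlier answers. The stated purpose is: "To minimise likelihood that respondents would look up answers and/or discuss the survey while taking it".

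**The concern.** The study evaluates the Guide as it was disseminated, months before the survey. The survey process can itself lead an HCP to open the Guide: the HCP is told of a survey about it, may be reminded twice, may be approached by liaison staff, and can choose when to respond within the open period. If that HCP then answers yes to Question 2, the answer is recorded as reading of the disseminated Guide.

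Two results are exposed. The reading rate could be too high as a measure of what dissemination achieved. In the stratified knowledge analysis, the reader group could mix HCPs who read the Guide in routine practice with HCPs who read it shortly before being tested on it.

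This cannot be left to the statistical analysis plan. Timing that was never asked for cannot be recovered at analysis.

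**Working it through.** **Could an existing provision separate the two kinds of reader?**
- Question wording and Table 9-1: no. Any yes counts, whenever the reading took place.
- Section 9.8: no. It covers look-up during the survey, not in the weeks between invitation and opening the survey.
- Section 9.11, stratification by time from distribution of the Guide to survey completion: no. It uses neither the invitation date nor the date of reading. An HCP who read the Guide last week but was sent it a year ago falls in the long-lag stratum.

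**The plan's own precision figure.** The Protocol gives no figure for receipt or reading. For scale, Section 9.7 gives 11.1 points at n = 50 and an observed 80%. The simple asymptotic formula reproduces it: 1.96 × √(0.80 × 0.20 / 50) = 0.1109, or 11.1 points. No stated figure depends on the wording of Questions 1 and 2.

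**Possible size.** Let p be the share of respondents who had read the Guide before the invitation, and q the share of the others who read it after the invitation and before answering. The Protocol gives neither, so both are assumptions. As worded, Question 2 estimates p + (1 − p)q; with a time anchor it would estimate p. The inflation is (1 − p)q.

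| p | q = 10% | q = 20% | q = 30% | q = 50% |
|---|---|---|---|---|
| 50% | 55% (+5) | 60% (+10) | 65% (+15) | 75% (+25) |
| 60% | 64% (+4) | 68% (+8) | 72% (+12) | 80% (+20) |
| 70% | 73% (+3) | 76% (+6) | 79% (+9) | 85% (+15) |
| 80% | 82% (+2) | 84% (+4) | 86% (+6) | 90% (+10) |

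The range is +2 to +25 points. The inflation equals 11.1 points at q = 0.111 / (1 − p): 22% for p = 50%, 28% for p = 60% and 37% for p = 70%.

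**Would excluding prompted readers recover the unprompted knowledge level?** Assume knowledge of 90% in readers and 70% in non-readers, and 50 respondents of whom 20 read the Guide early. Without any prompting, the composite would be (20 × 90 + 30 × 70) / 50 = 78%.
- 5 prompted, 25 non-readers: excluding the prompted gives (20 × 90 + 25 × 70) / 45 = 78.9%.
- 15 prompted, 15 non-readers: excluding the prompted gives (20 × 90 + 15 × 70) / 35 = 81.4%.

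Both exceed 78%, because exclusion removes HCPs who would otherwise have been non-readers.

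**The case against.** The strongest objections concern how far the point reaches, and most of them stand.

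- **No success claim is at stake.** A reader might infer that prompted reading would count as success of the dissemination. The Protocol does not support that: receipt and reading are descriptive, Section 8.2 states that there is no a priori hypothesis, and the 80% criterion in Section 9.2.1 applies to the knowledge composite, which does not use Questions 1 and 2.
- **The bias is not shown.** Nothing in the Protocol says whether or how often prompted reading occurs. The text of the invitation letter (Annex 2) was not available, so whether it names the Guide is unknown. The introduction that does name it appears only once the survey has been opened.
- **Not every respondent has the full window.** Three to six months is the field period, not each HCP's preparation time. Early responders get no reminder, and liaison contact is optional and reaches only some HCPs.
- **Question 1 is little affected.** Most of the sampling frame was already sent the Guide, and late opening does not change the fact of receipt. The exposure is mainly among HCPs added by supplementary outreach who obtain a copy after the invitation.
- **A shift of the composite across 80% cannot be concluded.** With the assumed 90% and 70%, a rise in reading from 40% to 50% moves the composite from 78% to 80%. The same assumptions with a rise from 60% to 70% give 82% to 84% and cross nothing. The crossing comes from the chosen inputs.

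What the objections leave intact is that the two kinds of reader are indistinguishable in the data, and that no analysis can separate them later.

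**Conclusion.** The point holds as a limited one. The wording of Question 2, and less so Question 1, leaves a possible upward bias of unknown size in the descriptive reading endpoint (and to a smaller degree receipt), and it blurs the planned reader versus non-reader stratification. The 2 to 25 points rest entirely on the assumed 50-80% prior readers and 10-50% prompted among the rest. Prompted reading could also raise knowledge scores, but the Protocol gives no basis for saying that it changes the primary result. No stated figure is wrong. The case for acting is that the change is cheap and can only be made before data are collected.

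**What to change.** Reword Question 2, and Question 1 in parallel: *Before you were invited to this survey, had you read (received) the Physician's Guide?* Offer four answers: *Yes*; *No, only after the invitation*; *No*; *I don't know*. In Table 9-1, count only *Yes* as read or received.

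In the stratification already planned in Section 9.9.1.2, report knowledge by three exposure groups: read before the invitation, read only after it, not read. Do not present the composite without prompted readers as the unprompted knowledge level; as shown above, that figure is biased upward.

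The cost is the wording and translation of two questions, one extra stratum that may be small at a target of 50 respondents, and a possibly lower reported reading rate. The change does not prevent prompted reading; it makes it visible. Answers remain self-reported, so the social desirability bias acknowledged in Section 9.11 applies to the new option too.

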9.2.1 Primary

The primary endpoint is knowledge levels of key information included in the ENJAYMO™ Physician's Guide across these 4 domains (assessed by 6 questions):

- Indication for CAD patients only (question 3)
- Important potential risks of serious infections including meningococcal infections (questions 4 and 6)
- Recommendations for vaccination of patients as per local regulations (question 5)
- Recommendations for monitoring and counseling patients to promote real-world safe-use conditions (questions 7 and 8).

The primary endpoint is a composite endpoint based on the percentages of HCPs with correct responses to questions included in the composite. The composite is the weighted average knowledge level across the core question set (6 questions) from the above domains. Success

criteria for the primary endpoint percentage is at least 80% of HCPs have answered the item correctly (if the number of HCPs who answered is at least 30).

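### Question 5, the only core item mapped to the vaccination domain, is a self-rating of familiarity scored as correct knowledge, and its key in Table 9-1 does not match its response options

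*Protocol*

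**What the plan says.** The primary endpoint is knowledge of the Guide's key information in four domains, measured by six core questions. Section 9.2.1 maps one domain to a single item: "Recommendations for vaccination of patients as per local regulations (question 5"). Question 4 goes elsewhere: "Important potential risks of serious infections including meningococcal infections (questions 4 and 6").

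In the Annex 3 questionnaire, question 5 reads "Are you familiar with current local guidelines or recommendations in patients with persistent complement deficiencies for meningococcal conjugate vaccine(s"), and its stem goes on to name "meningococcal serogroup B vaccine(s), and pneumococcal vaccine(s"). The options are yes, no and a don't-know answer. Question 4 puts a statement about vaccination before prescribing and asks for true, false or don't know.

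Table 9-1 describes what question 5 measures as "Knowledge of current local vaccine guidelines or recommendations in patients with persistent complement deficiencies" and derives it as "Checked “true” to question 5".

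Section 9.9.1.2 makes the composite an opportunity- or denominator-weighted percentage correct, to be judged against 80%.

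**The concern.** A knowledge item needs an answer that can be wrong. Nobody who answers yes to question 5 can be marked wrong, including a respondent who has the guideline content mistaken. The question also does not refer to the Guide, so someone who never saw it can truthfully say yes. The item is nevertheless labelled knowledge, counted in the primary composite, and reported singly as a knowledge level under the secondary endpoints.

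The Guide is meant, among other things, to increase vaccination. A report could therefore state that knowledge of the vaccination recommendations was above or below 80% when the figure is the share of respondents who call themselves familiar with local guidelines. No analysis can turn that answer into a test score afterwards. Section 9.8 also rules out going back to respondents about knowledge questions.

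**Working it through.** **The passages side by side.**

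| Place | Question 4 | Question 5 |
|---|---|---|
| Section 9.2.1, domain | Infection risk | Vaccination (sole item) |
| Annex 3, task | Judge a vaccination statement | Rate own familiarity |
| Annex 3, options | True / false / don't know | Yes / no / don't know |
| Table 9-1, key | 'true' | 'true' |

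The key fits question 4 and not question 5. The factual vaccination item sits outside the vaccination domain, and the non-factual one stands for it.

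**The plan's own figure.** Section 9.7 gives a 95% half-width of 11.1% for 50 respondents at 80%. The simple asymptotic formula gives 1.96 × √(0.80 × 0.20 / 50) = 0.111, so the figure reproduces. It is not in dispute; it concerns precision and says nothing about what an item measures.

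**Weight of question 5.** The protocol does not settle whether an opportunity is a question or a response row, so both cases are shown, each with equal denominators.

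- Six questions: 1/6 = 16.7%.
- Response rows counted from Annex 3: question 3 has 5, question 4 has 1, question 5 has 1, question 6 has 4, question 7 has 6 and question 8 has 6. The total is 23, so the weight is 1/23 = 4.3%.

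**Effect on the 80% criterion.** Let q be the proportion answering yes. The mean that the remaining items need is (0.80 × 6 − q)/5 with six items, and (0.80 × 23 − q)/22 with 23 rows. The protocol gives no value for q, so these are assumed values.

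| q (assumed) | Six items | 23 rows |
|---|---|---|
| 60% | (4.80 − 0.60)/5 = 84.0% | (18.40 − 0.60)/22 = 80.9% |
| 80% | 80.0% | 80.0% |
| 90% | (4.80 − 0.90)/5 = 78.0% | (18.40 − 0.90)/22 = 79.5% |
| 95% | (4.80 − 0.95)/5 = 77.0% | (18.40 − 0.95)/22 = 79.3% |
| 100% | (4.80 − 1.00)/5 = 76.0% | (18.40 − 1.00)/22 = 79.1% |

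A high yes rate lowers what the other items must reach by 2 to 4 points with six items, and by 0.5 to 0.9 points with 23 rows. A yes rate below 80% raises it.

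**The case against.** Several stronger readings are tempting, and the protocol does not support them.

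- **Vaccination knowledge is not measured at all.** Question 4 is a keyed vaccination item, is in the composite, and is reported singly like every other item. Questions 13 to 18 also cover vaccination practice, though only among prescribers (possibly 10 of 50) and again by self-report. What is missing is narrower: the item assigned to the domain tests no content, and knowledge of the local guideline content goes untested.
- **The composite is inflated.** The direction is not shown. Section 9.11 names social desirability bias, but it also cites a survey in which 28% to 97% of HCPs reported receiving and sometimes reading risk materials, and it argues that HCPs may answer such questions truthfully. That evidence concerns a different question, yet it is enough to stop one from assuming a high yes rate.
- **The key makes question 5 unscorable.** Applied literally, 'true' would give 0% on question 5, cap a six-item composite at 5/6 = 83.3% and require 4.80/5 = 96% on the rest. That would mean programming a response the questionnaire does not offer. The Annex 3 tick for this question is not visible in the text at hand and may well mark yes. The mismatch should be corrected, but it is not evidence of a capped endpoint.
- **Table 9-1 files question 5 under infection risk.** It appears so in the text, but the first cell of that row is blank and the table may have been broken in extraction. The point does not rely on it.
- **Question 5 gives away question 6.** Question 6 asks "which of the following warrant specific caution when using ENJAYMO™ (sutimlimab)? Please select all that apply", and respondents are told "Please note that you will only be able to move forward in the survey as you complete each question". But the preamble and questions 1 and 2 already name meningococcal infections, so the new cue is mainly pneumococcal, one of the four infections listed. Inflation of question 6 is not demonstrated.

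None of this answers the core point. Nothing elsewhere in the protocol makes question 5 a test of knowledge.

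**Conclusion.** The point holds in limited form. Under the section 9.2.1 mapping, the vaccination domain of the primary knowledge endpoint rests wholly on a self-rating, and the written scoring key for that item does not match its options. This does not depend on how the composite is weighted.

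The numerical effect on the composite does depend on the weighting and is modest. It runs from under 1 point to 4 points on the mean required of the other items if 90 to 100% answer yes, and it works in the opposite direction if fewer than 80% do. These figures assume equal denominators across items or rows and an assumed yes rate. The main harm is to interpretation: a self-rating would be reported as knowledge.

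**What to change.** In section 9.2.1 and Table 9-1:

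1. Take question 5 out of the core composite and report it descriptively as self-reported familiarity, with its key corrected to yes.
2. Map question 4 to the vaccination domain.
3. Restate the core set as five items (questions 3, 4, 6, 7 and 8), and carry the number through to section 8.1 and the synopsis, which also say six.

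These steps change no question, so they can be made even if the survey is already open. Section 6 planned data collection from Q2 2024, dependent on launch dates, and the protocol is dated 5 June 2024, so that is possible. In that case, make the change before anyone has seen the responses.

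If the survey has not launched, question 5 may instead be replaced by one factual item keyed to the vaccination text of the local Guide, which keeps six core items.

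The cost of the first route is one fewer core item, with infection risk then resting on question 6 alone. The cost of the second is one item to re-translate, possibly with country-specific keys because the domain refers to local regulations. Either way the composite may change slightly. Placing question 5 after question 6 is an optional minor step.

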B	Monitor patients for signs and symptoms of serious infections			
C	Take caution when prescribing ENJAYMO™ to patients who have chronic infections such as Hepatitis B, Hepatitis C or HIV			
D	Counsel patients about the risks of serious infection including meningitis			
E	Monitor patients for thyroid function			
F	Counsel patients about the risks of abnormal heart function			

8. According to recommendations in the “**ENJAYMO™ Physician’s Guide**,” you should counsel patients to seek immediate medical attention if they experience symptoms associated with risks of serious infections or meningococcal infections associated with ENJAYMO™ (sutimlimab). Please answer “True”, “False” or “I don't know/am not sure” to the following symptoms:

		True	False	I don't know/am not sure
A	Headache with stiff neck or back or confusion			
B	Fever, chills and rash			
C	Loss of appetite			
D	Muscle aches with flu-like symptoms			
E	Swelling in legs, ankles and feet			
F	Polyuria, dry mouth and blurred vision			

9. What is (are) the **primary source(s)** you use to learn about the appropriate indication, precautions for use, and potential risks for ENJAYMO™ (sutimlimab)? Please select all that apply. There are no correct/incorrect answers: **SELECT ALL THAT APPLY ANSWER – NO CORRECT RESPONSE.**

- Summary of Product Characteristics
- ENJAYMO™ Physician's Guide
- Professional Society or Congress
- The European Medicines Agency website
- Via specific discussions with Sanofi MSL
- Clinical practice guidelines; specify: _____
- Other (not listed above); specify: _____

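### The answer labels of core question 7 speak of monitoring, while three of its six items concern caution or counselling

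*Protocol*

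**What the plan says.** In Annex 3, the stem of question 7 asks "which of the following are important activities that are necessary when using ENJAYMO™ (sutimlimab". The two substantive columns are headed "Yes, needs to be monitored" and "No, does not need to be monitored"; a third column allows for not knowing or being unsure.

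The six items under these columns are of two kinds:

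- Items A, B and E are monitoring tasks, for example "Monitor patients for kidney damage" and "Monitor patients for signs and symptoms of serious infections".
- Item C reads "Take caution when prescribing ENJAYMO™ to patients who have chronic infections such as Hepatitis B, Hepatitis C or HIV". Item D is about counselling on serious infection, meningitis among the examples. Item F reads "Counsel patients about the risks of abnormal heart function".

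Table 9-1 (section 9.2.2) scores each item by a plain yes or no. It treats C as knowledge of caution and D as knowledge of counselling. It describes 7f as "Knowledge that patients do not need to be counselled to monitor heart function".

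Section 9.2.1 places question 7 among the six core questions of the primary composite, as one of two for the monitoring-and-counselling domain. The success criterion is 80%.

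**The concern.** For C, D and F, the option a respondent is shown does not name the thing being scored. An HCP who knows that patients should be counselled about serious infection earns credit on 7d only by ticking a column that says something needs to be monitored. A careful reader may see nothing to monitor and tick no or don't know, and either counts as not correct because don't-know answers stay in the denominator (Table 9-1 footnote; section 9.9.1.1).

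C and D are two of the three question 7 items keyed yes, so they carry safety messages that the survey is meant to test. Knowledge per question is also a secondary endpoint, where an error on 7c or 7d is not diluted by the other items.

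Nothing elsewhere in the protocol repairs this. The preamble tells respondents to review all the response choices, which sends them to these labels. Section 9.8 bars going back and bars contact to clarify knowledge answers. The language process in section 9.1.2 aims at faithful translation, so the German, Italian and Dutch versions would reproduce the mismatch. A second wave would use the same survey. No analysis plan could recover afterwards what a respondent meant.

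**Working it through.** **Items against labels**

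| Item | Activity | Label fits? | Keyed | Likely effect of a literal reading |
|---|---|---|---|---|
| A | monitoring | yes | no | none |
| B | monitoring | yes | yes | none |
| C | caution | no | yes | HCPs who know the message lost to no or don't know |
| D | counselling | no | yes | as for C; some who do not know it may tick yes because infection is monitored |
| E | monitoring | yes | no | none |
| F | counselling | no | no | HCPs who wrongly think counselling is needed may tick no and score correct |

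Three of six items are mismatched. Only C and D are plausibly pushed down. For F, a literal reading leads towards the keyed answer.

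**The plan's own precision figure (context only).** At n = 50 and 80% knowledge, section 9.7 gives 11.1 points. Check: 1.96 × √(0.8 × 0.2 / 50) = 0.111. It reproduces. The point does not depend on it.

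**Size of a loss on C and D.** Inputs:

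- True knowledge p = 80% (assumption, set at the target).
- Share m of HCPs who know the message but mis-tick: 20% to 40% (assumption; the protocol gives no figure).
- Scored sub-items in the core set, counted from Annex 3 for questions 3 to 8: 5 + 1 + 1 + 4 + 6 + 6 = 23.

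Formulas and results:

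- Item reading, p(1 − m): 0.8 × 0.8 = 64%; 0.8 × 0.6 = 48%. The loss per item, pm, is 16 to 32 points.
- Question 7 with partial credit, (2/6)pm: 5.3 to 10.7 points.
- Composite with six equally weighted questions, (1/6)(2/6)pm: 0.9 to 1.8 points.
- Composite with 23 equally weighted items, (2/23)pm: 1.4 to 2.8 points.

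At m = 5% the last figure is (2/23) × 0.8 × 5 = 0.35 points.

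**Offsetting gains.** Suppose 20% lack the knowledge behind an item and a share g of them are led to the keyed answer. Each affected item then gains 0.2g. On F alone, g of 20% to 40% gives 4 to 8 points, or 0.7 to 1.3 points on question 7. If C, D and F could all gain, the net effect is zero when 3 × 0.2g = 2 × 0.8m, that is g = 2.67m: about 13% when m = 5%, and 53% when m = 20%. With equal rates the net is downward. Above m = 37.5% no value of g could offset the loss. The documents give neither m nor g, so the sign is not established.

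**The case against.** The strongest reply is that the label is clumsy but workable. Both substantive columns open with a plain yes or no, the stem directly above asks what is necessary, and the key is yes or no throughout. A respondent who follows the stem gives the keyed answer on all six items, and one who does not know has a column for that. This stands. A reader might infer that correct knowledge cannot be expressed on half of question 7, or that any error on these items reflects the scale rather than the HCP. The documents support neither inference: the answer is ambiguous, not impossible, and only some errors would come from the label.

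A reader might also count all three mismatched items as losses and infer a fall of 10 to 20 points on question 7 (20% to 40% × 3/6). That requires every HCP to know the message and puts F on the wrong side, since F is keyed no.

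The wording of 7f in Table 9-1 could be taken as a scoring error, because it speaks of counselling to monitor while the item speaks of counselling about risks. It is not one. The scoring rule for 7f matches the questionnaire key, and other rows of the table paraphrase too.

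The reply does not remove the mismatch itself. It lies in the questionnaire text, and no safeguard in the protocol deals with it.

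**Conclusion.** The point holds as a measurement defect in one core question and should be corrected; it does not undermine the design. The labels fail to match the stem and items C, D and F. The resulting error is systematic, so a larger sample would not reduce it. Its net sign is uncertain and its effect on the composite is probably modest: a point or two, up to 2.8, under the illustrative rates, against a half-width of 11.1 points at n = 50. It would matter most if the composite fell close to 80%, and in the separate reporting of 7c and 7d.

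All sizes rest on assumed knowledge of 80%, an assumed mis-tick rate, partial credit within question 7, and one of two weightings. Section 9.9.1.2 describes an opportunity- or denominator-based weight, which fits the 23-item version more closely than an equal average of six questions.

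**What to change.** Relabel the question 7 columns *Yes, necessary* and *No, not necessary*, and keep the don't-know column. Apply this in every language version. The keyed answers stay as they are, and no clinical content changes.

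The cost is two column labels, plus a repeat of the independent proof-reading and local affiliate approval that section 9.1.2 requires for translations. Sample size is unaffected.

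Timing needs a check. The protocol is dated 05 June 2024, and section 6 plans the start of data collection for Q2 2024, depending on launch dates. If fielding has already started, a relabelled question creates two instrument versions, while section 9.9.1.1 pools both waves. In that case, record the version each respondent saw and report 7c, 7d and 7f by version.

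Optionally, bring the Table 9-1 description of 7f into line with the item text. This is editorial and changes no result.
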